6.3 Protocol Deviation

Protocol deviations including the types of deviations (eg, deviations in entry criteria, dosing, concomitant medications, procedurals, etc) will be summarized on the Enrolled Sample by trial center and prior treatment group. A listing of protocol deviations will also be provided.

A flagging variable taking values of "yes" or "no" will be created to indicate whether the deviation or violation was related to the COVID-19 pandemic.

7 Baseline Characteristics

7.1 Baseline Definition

An individual subject's baseline value is defined as the observation or assessment taken on the subject at the last visit of the double-blind treatment period in the parent trial. If a subject has separate screening visit(s) after end of the parent trial, then the last observation or assessment prior to the first dose of the open-label IMP will be considered

as baseline. For baseline values, there will be no imputation for missing or unknown values.

7.2 Demographic Characteristics

Demographic and baseline characteristics include age, sex, race, ethnicity, height, body weight, waist circumference, and body mass index (BMI). Demographic characteristics will be summarized on the Enrolled Sample by prior treatment group and for the overall analysis sample as well. Age, height, body weight, waist circumference and BMI will be treated as continuous variables, while sex, race and ethnicity will be treated as categorical variables. Refer to Section 10.4 for the conventions on using descriptive statistics for continuous and categorical variables.

7.3 Baseline Psychiatric Evaluations

Baseline psychiatric evaluations for this open-label extension trial are the ones taken at the last assessment visit of the parent trial. The baseline values in the following parameters will be summarized on the Enrolled Sample on the OC data using descriptive statistics: the ABC-I subscale score; all other ABC subscale scores; the CGI-S score;

Refer to Section 11 for the scales and the scoring via the aggregation of component items of the scales.

7.4 Medical and Psychiatric History

Medical history and psychiatric history data will be summarized on the Enrolled Sample by prior treatment group using descriptive statistics.

8 Safety Analysis

All safety analyses specified in this section will be performed on the Safety Sample. The baseline of a safety variable is defined as the last observation or assessment in the variable prior to the first dose of the open-label IMP.

Safety is the primary objective for this study. Safety will be assessed by the following standard endpoints for clinical trials and trials of antipsychotic drugs:

- The frequency and severity of treatment-emergent adverse events (TEAEs), serious TEAEs, and discontinuation from trial due to AEs.
- Change from baseline to post-baseline time points in: a) vital sign measurements; b) electrocardiogram (ECG) parameters; c) clinical laboratory tests (including prolactin) and urinalysis; and d) physical examination findings.

- Analysis of potential suicide events recorded on the Columbia-Suicide Severity Rating Scale (C-SSRS).
- Changes from baseline to post-baseline time points in results from extrapyramidal symptoms (EPS) scales (Simpson Angus Scale [SAS], Abnormal Involuntary Movement Scale [AIMS], and Barnes Akathisia Rating Scale [BARS]).
- Percentage of subjects with clinically significant changes in weight (gain or loss) from baseline to specified time points.
- Time to discontinuation.

8.1 Adverse Events (AEs)

All AEs will be coded by System Organ Class (SOC) and Preferred Term (PT) according to the latest version (Version 25.0 or newer) of Medical Dictionary for Regulatory Activities (MedDRA). A TEAE is defined as an AE that starts after the first dose of the open-label IMP or an AE that is present at baseline and increases in intensity or becomes serious or trial drug-related or results in death, discontinuation, interruption or reduction of the IMP. AEs occurring up to 30 days after the last dose of IMP in the open-label treatment period will be included in the AE summary tables. AEs having occurred 30 days after the last dose of IMP, if collected, will be listed only.

The incidence of the following AEs in Trial 331-201-00191 will be tabulated by prior treatment group and for the overall:

- a) TEAEs
- b) TEAEs by severity
- c) TEAEs potentially causally related to the IMP
- d) TEAEs with an outcome of death
- e) Serious TEAEs
- f) TEAEs leading to discontinuations of the IMP
- g) EPS-related TEAEs

The above summaries (b), (e) and (f) will also be prepared for TEAEs potentially causally related to the IMP.

In addition, TEAE incidence with rate $\geq 2\%$ at any SOC and PT levels in any of the two prior treatment groups will be provided. Incidence of TEAEs by SOC and PT will also be summarized for subgroups defined by sex, race, age, and body weight category at enrollment. Of note, AEs that are sex-specific, eg, ovarian cancer, will have the incidence rate evaluated for the specific sex.

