#### **Titration/Dosing Instructions:**

Subjects will follow the titration/dosing schedule in Table 3.2-1. As in the parent trial, the titration/dosing schedule will be based on body weight. Body weight at the Week 8 double-blind visit/baseline visit for Trial 331-201-00191 will be used to determine the starting dose. The body weight of the subject at this time will determine titration/dose requirements throughout the trial. Those subjects with body weight < 50 kg will receive a target dose range of 1 to 1.5 mg, and those subjects with body weight  $\ge 50 \text{ kg}$  will receive a target dose range of 1.5 to 3 mg.

Table 3.2-1 Open-label Titration/Dosing Schedule for Subjects with									
Irritability Associated with ASD a									
Trial Day	Number of Days on Brexpiprazole Dose IMP (Body Weight)								
		< 50 kg (QD)	≥ 50 kg (QD)						
Days 1 to 3	3	0.25 mg	0.5 mg						
Days 4 to 7	4	0.5 mg	1.5 mg						
Days 8 to 14	7	1 mg	2 mg						
Starting at Day 15	Based on investigator	1 or 1.5 mg	1.5, 2, or 3 mg						
(earliest opportunity to	discretion to change								
increase to maximum	dose based on								
dose within target dose	therapeutic effect or								
range)	tolerability								

QD = once daily.

<sup>aDose titrations will be performed in conjunction with a trial visit and therefore, trial visit windows are allowed for the titration schedule.

Subjects with body weight < 50 kg will receive brexpiprazole at a dose of 0.25 mg for Days 1 to 3, 0.5 mg for Days 4 to 7, and 1.0 mg for Days 8 to 14. Day 15 is the earliest opportunity that the investigator can increase to the maximum dose of 1.5 mg within the target dose range. The decision to increase the dose to 1.5 mg and when to increase the dose will be based on investigator judgment in order to reach a desired therapeutic effect.

Subjects with body weight  $\geq$  50 kg will receive brexpiprazole at a dose of 0.5 mg for Days 1 to 3, 1.5 mg for Days 4 to 7, and 2 mg for Days 8 to 14. Day 15 is the earliest opportunity that the investigator can increase to the maximum dose of 3 mg within the target dose range. The decision to increase the dose to 3 mg and when to increase the dose will be based on investigator judgment in order to reach a desired therapeutic effect.

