#### Immediately Reportable Event (IRE):

- Any SAE.
- Any AE related to occupational exposure.
- Potential serious hepatotoxicity case (see Section 5.4).
- Pregnancies are also defined as IREs. Although normal pregnancy is not an AE, it
  will mandate IMP discontinuation and must be reported on an IRE form to the
  sponsor. Pregnancy will only be documented on the AE page of the eSource if
  there is an abnormality or complication.

Clinical Laboratory Test Value Changes: It is the investigator's responsibility to review the results of all laboratory tests as they become available. This review will be

documented by the investigator's dated signature on the laboratory report. For each abnormal laboratory test result, the investigator needs to ascertain if this is an abnormal (ie, clinically significant) change from baseline for that individual subject. This determination, however, does not necessarily need to be made the first time an abnormal value is observed. The investigator may repeat the laboratory test or request additional tests to verify the results of the original laboratory tests. If this laboratory value is considered medically relevant by the investigator (subject is symptomatic, requiring corrective treatment or further evaluation), or if the laboratory value leads to discontinuation, and/or fulfills a seriousness criterion, this is considered an AE.

Severity: Adverse events will be graded on a 3-point scale and reported as indicated in the eSource. The intensity of an adverse experience is defined as follows:

**1 = Mild:** Discomfort noticed, but no disruption to daily activity.

**2 = Moderate:** Discomfort sufficient to reduce or affect normal daily activity.

**3 = Severe:** Inability to work or perform normal daily activity.

IMP Causality: Assessment of causal relationship of an AE to the use of the IMP is defined as follows:

**Related**: There is a reasonable possibility of a temporal and causal

relationship between the IMP and the AE.

**Not Related**: There is no temporal or causal relationship between the IMP and

the AE.

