# 5.2 Eliciting and Reporting Adverse Events

The investigator will periodically assess subjects for the occurrence of AEs. To avoid bias in eliciting AEs, subjects should be asked the non-leading question: "How have you felt since your last visit?" All AEs (serious and nonserious) reported by the subject must be recorded on the source documents and eSource provided by the sponsor. Serious AE collection is to begin after a subject has signed the ICF.

Use medical terminology in AE reporting. Adverse events should be reported as a single unifying diagnosis whenever possible or, in the absence of a unifying diagnosis, as individual signs or symptoms. Exacerbation or disease progression should be reported as an AE only if there are unusual or severe clinical features that were not present, or experienced earlier, or not expected based on the course of the condition. A reported AE

that undergoes a change in severity, seriousness, or toxicity should be reported as a new AE on the eSource.

Note: Normal pregnancy is not an AE and should not be recorded on the eSource; guidelines outlined in Section 5.5 should be followed for pregnancy reporting.

In addition, the sponsor must be notified immediately by telephone, fax, or e-mail of any IREs according to the procedure outlined below, in Section 5.3. Special attention should be paid to recording hospitalization and concomitant medications.

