- CT-8.2.4 Incidence of TEAEs by System Organ Class and MedDRA Preferred Term, by Sex (Safety Sample)
- CT-8.2.5 Incidence of TEAEs by System Organ Class and MedDRA Preferred Term, by Race (Safety Sample)
- CT-8.2.6 Incidence of TEAEs by System Organ Class and MedDRA Preferred Term, by Age Group (Safety Sample)
- CT-8.2.7 Incidence of TEAEs by System Organ Class and MedDRA Preferred Term, by Body Weight Group (Safety Sample)
- CT-8.2.8 Incidence of TEAE with Rate at Least 2% in Brexpiprazole Group by System Organ class and MedDRA Preferred Term (Safety Sample)

[figure not shown]
- CT-8.2.9 Incidence of Potentially Drug-Related TEAE with Rate at Least 2% in Brexpiprazole by System Organ class and MedDRA Preferred Term (Safety Sample)
- CT-8.2.10 Incidence of Potentially Serious TEAE with Rate at Least 2% in Brexpiprazole Group by System Organ class and MedDRA Preferred Term (Safety Sample)
- CT-8.2.11 Incidence of TEAE Resulting in Discontinuation of Study Medication with Rate at Least 2% in Brexpiprazole Group by System Organ class and MedDRA Preferred Term (Safety Sample)
- CT-8.2.12 Incidence of Deaths Due to TEAE with Rate at Least 2% in Brexpiprazole by System Organ class and MedDRA Preferred Term (Safety Sample)
- CT-8.3.1 Incidence of Potentially Drug-Related TEAEs by System Organ Class and MedDRA Preferred Term (Safety Sample)
- CT-8.3.2 Incidence of Potentially Drug-Related TEAEs by System Organ Class, MedDRA Preferred Term and Severity (Safety Sample)
- CT-8.4 Incidence of Deaths Due to TEAEs by System Organ Class and MedDRA Preferred Term (Safety Sample)
- CT-8.5.1 Incidence of Serious TEAEs by System Organ Class and MedDRA Preferred Term (Safety Sample)
- CT-8.5.2 Incidence of Serious TEAEs by System Organ Class, MedDRA Preferred Term and Severity (Safety Sample)
- CT-8.6.1 Incidence of TEAEs Resulting in Discontinuation from the Study Medication by System Organ Class and MedDRA Preferred Term (Safety Sample)
- CT-8.6.2 Incidence of TEAEs Resulting in Discontinuation from the Study Medication by System Organ Class, MedDRA Preferred Term and Severity (Safety Sample)
- CT-8.7 Incidence of TE EPS-related AEs by EPS Category and MedDRA Preferred Term (Safety Sample)
- CT-8.8 Incidence of Onset of Akathisia Adverse Event by Visit (Safety Sample)
- CT-8.9.1 Listing of TEAEs that Are Related or Probably Related to COVID-19 (Safety Sample)
- CT-8.9.2 Listing of Serious TEAEs or Deaths that Are Related or Probably Related to COVID-19 (Safety Sample)

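### A parent-trial AE that only becomes milder could be counted as an open-label TEAE, because Protocol 5.2 opens a new AE for any change in severity and SAP 8.1 does not link the records

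*SAP*

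**What the plan says.** **Recording rule.** Protocol 5.2 says that a reported AE "that undergoes a change in severity, seriousness, or toxicity should be reported as a new AE on the eSource". It gives no direction of change. Protocol 5.1 says "Adverse events will be graded on a 3-point scale and reported as indicated in the eSource" (mild, moderate, severe), so a step from moderate to mild is a change in severity.

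**TEAE definition.** SAP 8.1 has two routes joined by an or: "A TEAE is defined as an AE that starts after the first dose of the open-label IMP or an AE that is present at baseline". Route 1 is a start after that first dose. Route 2 continues: "or an AE that is present at baseline and increases in intensity or becomes serious or trial drug-related", or leads to death or to discontinuation, interruption or reduction of the IMP.

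**Rollover.** Under Protocol 3.2, open-label dosing begins the day after the last double-blind dose, so AEs can be ongoing on Day 1. Protocol 3.7.1.1 starts AE recording at consent for this trial and keeps the parent-trial medical history, updated where needed. It does not say how an ongoing parent-trial AE enters this database.

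**Use of the result.** SAP 8 lists TEAE frequency and severity first among the endpoints for the primary objective. SAP 8.1 tabulates TEAEs by prior treatment and overall, and adds a table of terms reaching 2% in either prior-treatment group. SAP 12 lists CT-8.8, a table of akathisia onset by visit.

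**The concern.** Route 2 shows the intent: an event already present at baseline should not count as treatment-emergent unless it gets worse or meets another stated criterion. The recording rule can defeat that intent. Once easing produces a new AE dated after the first open-label dose, that record satisfies route 1 and route 2 is never needed.

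Easing soon after rollover is conceivable here because every subject restarts at the bottom of the titration: "Subjects with body weight < 50 kg will receive brexpiprazole at a dose of 0.25 mg for Days 1 to 3", with 0.5 mg for heavier subjects. If dose-related AEs from the parent trial ease during those days, some of that improvement could appear as new events in the main safety tables, possibly to a different extent in the prior-brexpiprazole and prior-placebo columns.

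**Working it through.** The plan has no figure to reproduce: the trial is descriptive, and 119 is simply the parent trial's randomized number (SAP 4). The check is a logic test of the two rules, followed by scale.

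**Logic test.** TEAE = (record starts after first open-label dose) OR (present at baseline AND meets a route 2 criterion).

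| Course of an AE present at baseline | How it is recorded | TEAE? |
|---|---|---|
| Becomes milder | New record dated at the change | Yes, route 1 |
| Becomes milder | New record keeps the original onset | No |
| Becomes milder | Same record, or linked to it | No |
| Becomes worse | New record dated at the change | Yes, route 1 |
| Becomes worse | Same record, or linked to it | Yes, route 2 |

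The classification of a worsening event does not depend on the recording rule. The classification of an easing event does, and the documents do not settle which of its rows applies.

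**Weight of one subject.**
- Overall: 1/119 = 0.84 percentage points.
- Per column, assuming 60 (about half of 119; group sizes are not given): 1/60 = 1.7 points.
- Entry to the 2% table: 0.02 × 60 = 1.2, so two subjects are needed (2/60 = 3.3%). In a column of 50 or fewer, one is enough (1/50 = 2.0%).

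**Illustrative count.** The documents give neither the share of subjects with an AE ongoing at rollover nor the share of those AEs that step down a grade before resolving. If these are assumed to be 5% to 20% and 25% to 50%:
- low: 119 × 0.05 × 0.25 = 1.5 subjects;
- high: 119 × 0.20 × 0.50 = 11.9 subjects.

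These subjects would gain such a record; they do not all change a rate. If the 69.6% with a TEAE in Protocol 1.3 (pooled brexpiprazole trials) applied here independently, the effect on any-TEAE incidence would be 1.5 × 0.304 = 0.5 to 11.9 × 0.304 = 3.6 subjects. For a single preferred term, the offset depends on how often that same term recurs as a genuine new event, which the documents do not give.

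**The case against.** The best reply is that SAP 8.1 defines a TEAE by when the AE starts, not by when a record is opened. Carried-over akathisia that eases from moderate to mild is present at baseline, so the specific route should govern over the general one. That is a sensible reading, and probably what was meant. But Protocol 5.2 calls the changed event a new AE, the two routes are alternatives, and nothing in SAP 8.1 gives route 2 precedence. SAP 1 says the SAP sets out algorithms and conventions in detail. SAP 8.7 states that a subject is counted once for overall suicidality, whereas 8.1 has no corresponding rule for split AE records.

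Two further objections stand as limits. The onset date of the new record is not stated; if it keeps the pre-dose onset, no false TEAE arises. Nor is it stated how parent-trial AEs enter the database; if they enter only as medical history, easing is not a change in a reported AE. The point is therefore that such an event could be counted, not that it will be.

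A reader might also infer that CT-8.8 will show new onsets at visits where akathisia was resolving. Only its title is given, and no text says whether it counts first onsets or every record, so this is possible but not established.

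Finally, no inference is planned, the full system organ class and preferred term tables are produced alongside the 2% table, and any error overcounts TEAEs, which is the cautious direction for a safety trial. That limits the consequence but does not make the table correct.

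**Conclusion.** The concern holds as a conflict between two stated rules: Protocol 5.2 treats a decrease in severity as a new AE, and SAP 8.1 route 1 can then count it against the evident purpose of route 2. It rests on two conditions that the documents leave open: the new record is dated at the change, and the parent-trial AE is carried into this trial's AE data.

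The size cannot be derived. What can be said is that each affected subject is worth 0.84 points of 119, or about 1.7 points of an assumed column of 60, and only where that subject has no other TEAE in the term or category.

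A reader might infer a substantial inflation of the prior-brexpiprazole column, or from the 7.3% akathisia rate in Protocol 1.3 that a couple of easing akathisia cases should be expected there. The documents do not support either. That rate is the proportion reporting akathisia at any time in pooled trials, not akathisia ongoing at rollover at a grade from which it could ease. No figure is given for ongoing AEs or for easing. The column size of 60 is also generous, since only consenting, eligible completers enter.

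**What to change.** Add to SAP 8.1:

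*Records opened because a reported AE changed in severity are linked to the original AE and treated as one event with the original onset date. If that event was present before the first open-label dose, it is a TEAE only if its severity exceeds the baseline grade or it meets another criterion of the second limb (becomes serious or drug-related, or results in death, discontinuation, interruption or reduction of IMP). CT-8.8 uses the first onset of the linked event.*

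The exception for the other second-limb criteria is needed. Without it, an AE that eased and later became serious or led to discontinuation would be lost. The wording also means that a baseline AE that eases and then returns to its baseline grade is not a TEAE; the sponsor should confirm that this is intended.

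Alternatively, limit the new-record rule in Protocol 5.2 to increases in severity or seriousness and record decreases as updates to the existing AE.

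Either way, the sponsor should state how AEs ongoing from the parent trial enter this database. The cost of the SAP route is one derivation (same preferred term, contiguous dates, changed grade) or one link field. No new data from subjects are needed, and it can be done before database lock.

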8.2 Clinical Laboratory Tests

During the open-label treatment period, clinical laboratory assessments, including hematology, serum chemistry, urinalysis, serum bicarbonate, glycosylated hemoglobin (HbA1c), serum prolactin concentrations, thyroid stimulating hormone (TSH), and free T4 (if the TSH is abnormal) will be made in office at the Week 14 and 26 visits. Coagulation parameters will be assessed only at the end timepoint (the Week 26 visit) of the open-label treatment period. Of note, metabolic parameters (ie, total cholesterol, low density lipoprotein (LDL), high density lipoprotein (HDL) and triglycerides) and serum glucose will be separately summarized for fasting and non-fasting tests, and serum prolactin concentrations will be separately summarized for male and female subjects.

The assessment value and the change from baseline value at each of the specified visits above in each of the above-mentioned clinical laboratory parameters will be summarized on the OC data by using the descriptive statistics for continuous variables. Likewise, the summary statistics will also be computed on the LOCF data for the last assessment visit.

Potentially clinically relevant laboratory measurement test results during the open-label treatment period will be identified and the number and percentage of subjects who had such a laboratory value will be tabulated by laboratory parameter and prior treatment group based on the observation from the scheduled and the unscheduled (if any) post-baseline visits. Criteria for Identifying Laboratory Values of Potential Clinical Relevance for the children and adolescent subjects enrolled into this study are provided in Appendix 2.

Potential serious hepatotoxicity is an immediately reportable adverse event of interest. The case of potential serious hepatotoxicity at a post-baseline visit is defined as having (1) aspartate aminotransferase (AST) or alanine aminotransferase (ALT) that is ≥ 2 times the upper limit of normal (ULN), and (2) the total Bilirubin ≥ 1.6 times the ULN. The incidence of potential serious hepatotoxicity (ie, the number and percentage of subjects who had a case of potential serious hepatotoxicity) will be tubulated by prior treatment group based on the observation from the scheduled and the unscheduled (if any) post-baseline visits.

All potentially clinically significant laboratory abnormalities will be listed by prior treatment group, patient ID, baseline value, age, sex, body weight, visit, and dose at onset of the event if applicable.

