### 3.7 Trial Procedures

Trial assessment time points are summarized in Table 3.7-1.

Table 3.7-1	Schedu	ile of Ass	essmen	ts - Rollo	ver Subje	ects from	Trial 3	331-201-0	0148			
	Screening/	26-week Open-label Treatment Period						ЕОТ	Follow- up			
Assessment	Baseline  Last visit from Trial 331-201-00148/ Baseline for Trial 331-201-00191	Week 1 (Day 7 dl ± 2 days)	Week 2 (Day 14 ± 2 days)  In office	Week 3 (Day 21 ± 2 days)  Virtual or In office	Week 4 (Day 28 ± 2 days)  Virtual or In office	Week 8 (Day 56 ± 2 days)  Virtual or In office	Week 14 (Day 98 ± 2 days) In office	Week 18 (Day 126 ± 2 days)  Virtual or In office	Week 22 (Day 154 ± 2 days) Virtual or In office	Week 26/ET (Day 182 ± 2 days) In office	21 (± 2) days after last dose of IMP By Tele phone	Notes
Informed	X											Section 3.4.1
consent/assent, update medical history, as needed												
Prior medications	X											Section 3.7.4
Inclusion/exclusion criteria	X											
CGI-S	X	X	X	X	X	X	X	X	X	X		Section 3.7.2.2
SAS, AIMS, & BARS	X		X				X			X		Section 3.7.3.5
C-SSRS	X	X	X	X	X	X	X	X	X	X		Section 3.7.3.5.4
ABC	X	X	X	X	X	X	X	X	X	X		Section 3.7.2.1
CCI												
Physical examination	X									$\overline{X}$		Section 3.7.3.3.1
Body weight and waist circumference	X						X			X		Section 3.7.3.3.1
Height	X						X			X		Section 3.7.3.3.1
Vital signs	X	X	X	X	X	X	X	X	X	X		Section 3.7.3.3.2

Table 3.7-1	Schedu	ıle of Ass	essment	ts - Rollo	ver Subje	ects from	Trial 3	31-201-0	0148			
	Screening/ Baseline Last visit from Trial 331-201- 00148/ Baseline	26-week Open-label Treatment Period							ЕОТ	Follow- up		
Assessment		Week	Week 2 (Day 14 ± 2 days)	Week 3 (Day 21 ± 2 days)	Week 4 (Day 28 ± 2 days)	Week 8 (Day 56 ± 2 days)	Week 14 (Day 98 ± 2 days)	Week 18 (Day 126 ± 2 days)	Week 22 (Day 154 ± 2 days)	Week 26/ ET (Day 182 ± 2 days)	21 (± 2) days after last dose of IMP	Notes
	for Trial 331-201- 00191	Virtual or In office	In office	Virtual or In office	Virtual or In office	Virtual or In office	In office	Virtual or In office	Virtual or In office	In office	By Tele phone	
ECG	X						X		I	X		Section 3.7.3.4
Clinical laboratory	X						X			X		Section 3.7.3.2
tests (hematology, serum chemistry, and urinalysis)												
HbA1c	X						X			X		Section 3.7.3.2
Prolactin	X						X			X		Section 3.7.3.2
Urine pregnancy test	X						X			X		Section 3.7.3.2
ACTH	X									X		Section 3.7.3.2
Cortisol	X									X		Section 3.7.3.2
TSH with reflex to free T4 if abnormal	X						X			X		Section 3.7.3.2

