5.2 Handling of Missing Data

For scoring via the aggregation of component items of the efficacy and safety scales, and how to handle the items with unrecorded (missing) ratings for the scoring, refer to Section 11 for details.

The Observed Case (OC) dataset for the parameters (eg, efficacy or safety variables) of interest will consist of all the actual observations or assessments of the parameters recorded at the visits during the open-label treatment period and the follow-up period. Note that if observations or assessments are unrecorded, thus missing, at a visit, the missing values will not be imputed. Subjects discontinued from treatment before Week 26 will have an ET visit where all assessments originally scheduled for the Week 26 visit will be made. Such data collected at the ET visit (or any other unscheduled visits, if any) will be mapped to a specific visit per the visit window algorithm given in Section 10.3. In the instances where a subject discontinues the treatment early but somehow does not subsequently attend the ET visit, all scheduled assessments after the timepoint of his or her treatment discontinuation will remain missing. All by-visit analysis (including summary) will be based on the OC dataset.

The Last-Observation-Carried-Forward (LOCF) dataset include all OC data and in addition the imputed data per a commonly used imputation rule (the LOCF rule) as follows: If no observation or assessment is recorded at a scheduled visit, the missing value for that visit will be imputed by carrying forward the last available (ie, the immediately preceding) observation or assessment (inclusive of the value at an ET visit, if any). Note that baseline data cannot be carried forward to impute post-baseline values.

Of particular interest is the timepoint of the end-of-trial visit at Week 26. Serving as a kind of supplementary evidence for the results, the analysis will be repeated on the Week 26 LOCF data for each analysis performed on the Week 26 OC data.

6 Study Conduct

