10.4 Descriptive Statistics for Continuous and Categorical Variables

For continuous variables, descriptive statistics include N (which is number of subjects with non-missing value), mean, standard deviation, median, quartile, minimum and maximum. For categorical (eg, nominal or dichotomous) variables, descriptive statistics refer to frequency distribution (eg, count and percentage). Unless stated otherwise, ordinal variables such as assessment scores on all the scales used for this trial will be treated as continuous. Wherever possible, inferential statistics will be accompanied by descriptive statistics for presentation. Descriptive statistics can be used alone for data summary purpose, for example, for summarizing baseline demographic characteristics, medical history, etc. Unless specified otherwise, the denominator used for calculating percentage will be the number of unique subjects in the analysis sample (or its subgroups). And whenever applicable, a row of "Missing/Unknown" will be presented along with rows of recorded outcomes for the tabulation of the categorical variables.

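### Free T4 is measured only when TSH is abnormal, yet SAP 8.2 plans its change from baseline and an LOCF last-visit summary with no exception for a test that was not indicated (minor).

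*SAP*

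**What the plan says.** Table 3.7-1 in Protocol 3.7 schedules "TSH with reflex to free T4 if abnormal" at screening/baseline, Week 14 and Week 26/ET. SAP 8.2 keeps the condition. Its list of Week 14 and Week 26 tests closes with "thyroid stimulating hormone (TSH), and free T4 (if the TSH is abnormal) will be made in office at the Week 14 and 26 visits".

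The next paragraph of SAP 8.2 says that the value and the change from baseline "in each of the above-mentioned clinical laboratory parameters will be summarized on the OC data by using the descriptive statistics for continuous variables". It adds: "Likewise, the summary statistics will also be computed on the LOCF data for the last assessment visit". Free T4 is in the list and nothing exempts it. SAP 10.4 defines the statistics as "N (which is number of subjects with non-missing value), mean, standard deviation, median, quartile, minimum and maximum".

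SAP 5.2 sets the LOCF trigger: "If no observation or assessment is recorded at a scheduled visit, the missing value for that visit will be imputed by carrying forward" the latest available value. Baseline values may not be carried forward.

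Baseline is worded in two ways. SAP 7.1 takes the value at the last double-blind visit of the parent trial (or the last one before dosing if there was a separate screening visit) and does not impute a missing one. The opening of SAP 8 takes the last observation of the variable before open-label dosing.

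**The concern.** For most analytes an empty cell means that a sample was missed. For free T4 it usually means that TSH was normal, so the test was not needed. The SAP treats both cases alike.

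First, a change needs two free T4 values, and so in general an abnormal TSH both before dosing and at the visit. The change row therefore describes children whose thyroid test was already abnormal at entry, whereas a safety reader mainly wants to see abnormality that begins on drug.

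Second, an absent free T4 at Week 26 points to a normal TSH. LOCF replaces it with a value taken when TSH was abnormal. The error runs in one direction: it keeps the earlier abnormal episode in a row labelled as the last visit.

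**Working it through.** The documents state no figure on this point, so there is none to reproduce. The check has two parts.

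**What the rules give for each TSH pattern** (main schedule, baseline as in SAP 7.1)

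| TSH at baseline / Week 14 / Week 26 | Free T4 observed | Change from baseline | LOCF last-visit value |
|---|---|---|---|
| normal / abnormal / abnormal | Weeks 14, 26 | none | Week 26 |
| normal / abnormal / normal | Week 14 | none | Week 14, carried |
| abnormal / abnormal / normal | baseline, Week 14 | Week 14; carried to last visit | Week 14, carried |
| abnormal / normal / normal | baseline | none | none |
| abnormal / abnormal / abnormal | all three | Weeks 14, 26 | Week 26 |

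The first two rows are new-onset cases and give no change. The second and third rows put a Week 14 value into the last-visit summary although TSH was normal at Week 26.

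**How many subjects this could involve**

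Inputs:
- N = 119, the ceiling in SAP 4. Full attendance is assumed.
- p, the chance that TSH is abnormal at a visit: 2.5%, 5% or 10%. This is an assumption; the documents give no rate.
- r, the within-subject correlation of abnormality between two visits: 0, 0.7 or 1. This is also an assumption. The same p and r are used for every visit and pair of visits.

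Formulas:
- P(both) = p² + r·p·(1 − p)
- paired changes at a visit = N·P(both)
- Week 14 values carried to Week 26 = N·(p − P(both))
- size of the Week 26 LOCF set = N·(2p − P(both))

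Example, p = 5% and r = 0.7: P(both) = 0.0025 + 0.7 × 0.0475 = 0.03575. Paired changes = 119 × 0.03575 = 4.25. Carried = 119 × 0.01425 = 1.70. LOCF set = 119 × 0.06425 = 7.65. Carried share = 1.70 / 7.65 = 22%.

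| p | r | Free T4 values per visit | Paired changes | Carried | LOCF set | Carried share |
|---|---|---|---|---|---|---|
| 2.5% | 0 | 2.98 | 0.07 | 2.90 | 5.88 | 49% |
| 2.5% | 0.7 | 2.98 | 2.10 | 0.87 | 3.85 | 23% |
| 2.5% | 1 | 2.98 | 2.98 | 0 | 2.98 | 0% |
| 5% | 0 | 5.95 | 0.30 | 5.65 | 11.60 | 49% |
| 5% | 0.7 | 5.95 | 4.25 | 1.70 | 7.65 | 22% |
| 5% | 1 | 5.95 | 5.95 | 0 | 5.95 | 0% |
| 10% | 0 | 11.90 | 1.19 | 10.71 | 22.61 | 47% |
| 10% | 0.7 | 11.90 | 8.69 | 3.21 | 15.11 | 21% |
| 10% | 1 | 11.90 | 11.90 | 0 | 11.90 | 0% |

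Paired changes thus run from about 0 to 12. The two problems trade off: when abnormality persists there are more pairs and fewer carried values. Incomplete rollover, dropout and the split by prior treatment in SAP 10.5 make every count smaller.

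**The case against.** A reader might infer that thyroid abnormality starting on drug goes unreported, or that the laboratory part of the primary safety endpoint is wrong. The documents support neither.

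- SAP 8.2 also tabulates and lists laboratory values of potential clinical relevance from scheduled and unscheduled post-baseline visits. Appendix 2 gives TSH and free T4 limits by age as absolute levels, so no baseline is needed. Tables CT-10.2.1 to CT-10.2.3 carry these results. TSH change from baseline is summarised as well.
- It would be too strong to say that a new-onset case can never give a change. The SAP 8 baseline wording could admit an older free T4 from before dosing, if one exists, though its timing would not match.
- Carrying Week 14 forward does not arise for subjects followed on the COVID-19 Addendum schedules (Tables 1.2-1 and 1.2-2), which have no Week 14 TSH.
- N is shown beside each mean, the trial is descriptive, and SAP 5.2 calls the Week 26 LOCF repeat supplementary.

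All of this stands, and it limits the point to a few rows.

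It can also be argued that a programmer would treat an unreflexed test as not applicable. That is possible, but SAP 5.2 does not say so. Its condition, "If no observation or assessment is recorded at a scheduled visit", turns only on whether a value exists. The displayed N shows that a row is sparse; it does not show which values were carried past a normal TSH.

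**Conclusion.** The point holds as a minor one. SAP 8.2 read with SAP 5.2 gives a free T4 change row restricted to subjects tested both before dosing and at the visit. It also gives an LOCF row in which some last-visit values are Week 14 values from children whose Week 26 TSH was normal. Both follow from the text and need no assumption about rates.

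The size is unknown. Under the assumed rates and at the ceiling of 119, there would be about 0 to 12 paired changes. Carried values would make up 21% to 49% of the LOCF set for correlations of 0 to 0.7, and none if abnormality fully persisted. No test or decision rests on these rows, and abnormal thyroid values remain visible elsewhere in the planned output.

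**What to change.** In SAP 8.2:

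- Exclude free T4 from the change-from-baseline and LOCF summaries.
- State that a free T4 not reflexed because TSH was normal is *not applicable* rather than missing.
- Report observed free T4 with the concurrent TSH at each visit. Use either a small table of TSH category by free T4 category, including *not reflexed*, or a listing with counts.
- Keep TSH in the change-from-baseline tables.

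The small table would add something: the shift tables planned in SAP 12 (CT-10.4.1 to CT-10.4.4) cover chemistry, hematology, urinalysis and prolactin, and none is named for thyroid tests.

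The cost is a few lines of SAP wording and one small table or listing from data already collected. No visit, sample or protocol change is needed.
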